4 OBJECTIVES AND ENDPOINTS

4.1 *Objectives*

4.1.1 **Primary Objective**

To evaluate the safety and tolerability of OCR-002 in patients with acute liver failure/severe acute liver injury.

Hypothesis: Treatment with OCR-002 is safe and tolerable in patients with acute liver failure/acute liver injury.

4.1.2 **Secondary Objectives**

To evaluate the steady state pharmacokinetic and pharmacodynamic profile of OCR-002 in patients with impaired and minimal renal dysfunction using urinary PAGN as a surrogate marker.

Hypothesis: A dose of 10-20g/24h (0.42-.83g/h) will achieve steady state plasma concentrations within 6-12h with little additional accumulation in the ALI/ALF setting.

To evaluate the effect of OCR-002 on ammonia levels in patients with acute liver failure/severe acute liver injury.

Hypothesis: Treatment with OCR-002 will reduce ammonia levels in patients with ALI/ALF.

To evaluate the effect of OCR-002 on neurological function in patients with acute liver failure/severe acute liver injury.

Hypothesis: Treatment with OCR-002 will improve neurological function in patients with acute liver failure/severe acute liver injury.

4.2 *Endpoints*

4.2.1 **Safety Endpoints**

Safety assessments will include: abbreviated physical examinations, vital signs (blood pressure, pulse rate, respiration rate, and body temperature), clinical laboratory tests (hematology and serum chemistry), 12-lead ECGs, and reported and observed adverse events.

4.2.2 **Exploratory Efficacy Endpoints**

- Ammonia concentrations.
- Neurological assessment will be measured by the Glasgow Coma Scale, the West Haven Criteria, and the Orientation log (O-log) (34).

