6.2 Selection Criteria

6.2.1 Inclusion Criteria

1. Men and women, ages 18-65 (have not reached their 66th birthday).
2. Acute liver failure, defined as the development of coagulopathy (International normalized ratio [INR] ≥ 1.5) with encephalopathy in a patient with no prior history of liver disease, with onset of symptoms within 28 days of the inciting event. Patients may have either a history of acetaminophen overdose (defined as >4 g/day within 7 days of presentation) and/or detectable acetaminophen levels in the serum, with a pattern of liver function tests typical for acetaminophen toxicity (bilirubin < 10 mg/dL and alanine aminotransferase (ALT) ≥ 1000 IU/L), or a diagnosis of hepatitis A, hepatitis B, drug-induced liver injury, autoimmune hepatitis or indeterminate cause based on standard criteria. Standard criteria for these diagnoses are as follows:
 - hepatitis A, defined as positive anti-HAV IgM;
 - hepatitis B, defined as positive anti-HBc IgM and positive HBsAg;
 - autoimmune hepatitis, defined as follows:
 - Globulins elevated $> 1.5X$ ULN;
 - ANA, ASMA or LKMA positive in titer of at least 1:80;
 - Negative serology for viruses associated with acute or chronic hepatitis; and/or

- Liver biopsy showing CAH;
- drug-induced liver injury, defined as presumed injury by a likely agent, with other causes excluded; or
- indeterminate cause, defined as
 - the exclusion of all the diagnoses listed in the Selection Criteria (see Section 6.2), including:
 - Budd-Chiari;
 - Hepatitis C, E, delta, drug-induced hepatitis;
 - mushroom intoxication; and
 - other viruses, defined as follows:
 - HSV: anti-HSV IgM positive and anti-HSV IgG negative and four fold increase between acute and convalescent sera and HSV seen in liver tissue;
 - EBV: anti-EBV IgM or EBV seen in liver tissue; and
 - CMV: anti-CMV IgM positive and anti-CMV IgG negative and four fold increase between acute and convalescent sera or CMV seen in liver tissue.

3. ALI patients may also be enrolled (those meeting the above criteria plus coagulopathy (INR \geq 2.0) and no evidence of encephalopathy).
4. Written informed consent from the patient (ALI) or patient's legally authorized representative or family member if he/she is considered encephalopathic (ALF).
5. Ammonia level \geq 60 μ mol/L at baseline (within 8h prior to T0/initiation of infusion).
6. Serum creatinine levels as follows:
 - a. Cohort 1: Creatinine \leq 1.5 mg/dL; and

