6.3 Informed Consent and Enrollment

6.3.1 Informed Consent

The Investigator will select patients in accordance with eligibility criteria detailed in Section 6.2. Prior to the study, for patients with ALF, the patient's legally authorized representative or family member will receive a comprehensive explanation of the proposed treatment including the nature and risks of the study, any known AEs, the investigational status of the components, and the other elements that are part of obtaining proper informed consent. The patient and/or the patient's legally authorized representative or family member will also receive a detailed explanation of the proposed use and disclosure of their protected health information. After having the nature and risks of the study explained to them, the patient and/or the legally authorized representative or family member will be allowed sufficient time to consider participation in the study. Patients who meet criteria for ALI are, by definition, not encephalopathic and will be able to consent for enrollment without additional consents being obtained from a legally authorized representative or family member, although both consents may be obtained.

For those with ALF, the patient's legally authorized representative or family member must provide written informed consent and provide authorization to disclose the patient's protected health information in order to enroll in the study. The informed consent process will be conducted per institutional protocol and in compliance with applicable IRB requirements. Written informed consent must be obtained from the patient's legally authorized representative or family member before any study related activities are conducted. The Investigator must retain all original signed and dated informed consent forms (ICF's) (together with any subsequent IRB-approved amended versions) in the patient's file. A copy of the original signed and dated ICF (and any amendments) must be provided to the patient and/or the patient's legally authorized representative or family member.

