11.2 Comparisons of Interest

Collected data will be evaluated overall and by cohort (patients with minimal renal dysfunction and those with compromised renal function).

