11.6 Statistical Analyses

Tables and listings will be produced using SAS v9.2 or higher (SAS, Cary, NC). Data summaries by cohort group will be presented. For continuous variables, data will be summarized with the number of patients, mean, standard deviation, median, and minimum and maximum overall and by cohort. For categorical variables, data will be tabulated in frequency tables to display the number and proportion of patients for each category overall and by cohort. Baseline assessments for each outcome variable will be defined as the last measurement obtained before treatment initiation. Each point estimate will be presented with 2-sided 95% confidence intervals and all statistical tests will use a two-sided 5% significance level.

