11.7.2 Clinical Laboratory Tests

Clinical laboratory test parameters will be listed for individual patients. Baseline for clinical laboratory parameters will be defined as the last evaluation before the start of the initial dosing with study drug. Summary statistics, including mean absolute change from baseline, will be calculated for each parameter and summarized.

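### Section 11 plans no within-patient change or shift summary for the neurological scales, so its frequency tables do not show how many patients with encephalopathy improved

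*Combined protocol and SAP*

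**What the plan says.** The secondary hypothesis in protocol Section 4.1.2 is "Treatment with OCR-002 will improve neurological function in patients with acute liver failure/severe acute liver injury". It covers ALF and ALI together. Section 4.2.2 lists Glasgow Coma Scale, West Haven and O-log as exploratory efficacy endpoints. It gives no change score, responder rule or key time point.

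The two diagnoses enter in different neurological states. Inclusion criterion 2 in Section 6.2.1 requires encephalopathy for ALF. Criterion 3 adds that "ALI patients may also be enrolled", and Section 6.3.1 says "Patients who meet criteria for ALI are, by definition, not encephalopathic". No quota, cap or expected ALI share is given, and each renal cohort takes both diagnoses (Section 5.1).

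For analysis, Section 11.2 states "Collected data will be evaluated overall and by cohort", where cohort means renal function. For categorical variables, Section 11.6 says "data will be tabulated in frequency tables to display the number and proportion of patients for each category overall and by cohort". It also says "Tables and listings will be produced using SAS v9.2 or higher" and "Baseline assessments for each outcome variable will be defined as the last measurement obtained before treatment initiation". Sections 11.7.1 to 11.7.6 cover adverse events, laboratory tests, vital signs, ECG, physical examination and pharmacokinetics; none covers the neurological scales. The memorandum at the end of the document confirms that no separate SAP was compiled. Section 11.4 makes the per-protocol (PP) population primary for all outcomes, with the ITT population as sensitivity analysis.

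**The concern.** A hypothesis of improvement is about what happens to a patient relative to that patient's own starting point. The planned output for a graded scale such as West Haven is a set of counts at each visit, overall and by renal cohort. That output has two weaknesses.

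- It does not link a later grade to the same patient's baseline grade. Movements in opposite directions cancel, and the number who improved cannot be read off.
- It includes patients with no encephalopathy at baseline, who cannot improve on West Haven. They are probably near the ceiling on the other two scales as well, though that is an inference.

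At stake is whether the description answers the question in Section 4.1.2. No safety conclusion, error rate or dose decision depends on it.

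**Working it through.** **Inputs from the documents.** Up to 36 evaluable patients, about 18 per cohort (Section 5.1). Summaries overall and by renal cohort (11.2, 11.6). Neurological battery within 8 h before the infusion starts (8.2), then repeated on treatment (8.3).

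**Inputs assumed.** The share without encephalopathy at baseline, g, is not stated; 10%, 30% and 50% are used. The improvement rate among encephalopathic patients, p, is not stated; 60% is used. The West Haven grades are not printed in the protocol; that no encephalopathy is the best grade is taken from the scale's ordinary meaning.

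**The plan's own figure.** There is none for this endpoint, and Section 11.3 reports no sample size calculation. The only size figure that can be checked is enrolment: 36/(1 − 0.25) = 48, consistent with the stated ceiling of 50. It does not bear on this point.

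**Step 1: what the frequency tables carry.** For any grade,

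count at visit = baseline count − patients leaving the grade + patients entering it.

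Only the net is shown. If equal numbers move up and down between the same two grades, the table at the visit is identical to the one at baseline. The number improved is therefore not determined by these tables, whatever g is.

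**Step 2: a pooled improvement rate, if one were reported.** Patients without baseline encephalopathy add to the denominator and nothing to the numerator:

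pooled rate = (1 − g) × p + g × 0 = (1 − g)p, with a ceiling of 1 − g.

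| g (assumed) | Ceiling | Reading when p = 60% |
|---|---|---|
| 10% | 90% | 0.90 × 0.60 = 54% |
| 30% | 70% | 0.70 × 0.60 = 42% |
| 50% | 50% | 0.50 × 0.60 = 30% |

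**Step 3: means.** The same dilution applies. An assumed mean fall of 1.0 grade among encephalopathic patients, with g = 50% and the others unchanged, reads 0.5 × 1.0 = 0.5 grade pooled.

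**Step 4: can the rate be recovered?** Yes, if data are complete. The planned baseline frequency table gives g, and dividing returns p: 42%/70% = 60%. This undoes Step 2 for a reported rate. It does not undo Step 1, because no improvement count is planned in the first place.

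**Step 5: cost in precision.** Suppose 10 of 18 patients in a cohort are encephalopathic at baseline and 6 improve. Pooled, this is 6/18 = 33% (Clopper-Pearson 95% CI 13% to 59%). Restricted, it is 6/10 = 60% (26% to 88%).

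**The case against.** The strongest case against is that the figures describe an output the plan does not contain. No proportion improving is planned, and both g and p are assumed. If such a proportion were reported, the baseline table would let a reader rescale it. This stands. It reduces the numbers in Step 2 to illustration; what is left is the missing link to baseline in Step 1.

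A reader might infer that pooling would create a false difference between renal cohorts. With 10/18 and 15/18 encephalopathic and 60% improving in each, the cohorts read 6/18 (33%) and 9/18 (50%). But that example needs a five-patient imbalance. If both cohorts share the same g, an imbalance of five or more in the number without encephalopathy arises by chance in about 1%, 10% or 13% of trials at g = 10%, 30% or 50%. Even then Fisher's p is 0.50. The documents state no between-cohort neurological hypothesis, so this reading is not supported.

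A reader might also infer deliberate neglect from Section 11.7.2, which for laboratory tests promises "Summary statistics, including mean absolute change from baseline, will be calculated for each parameter and summarized", with like wording for vital signs and ECG. Those subsections sit under safety, and change in ammonia is not named either. The omission looks like the brevity of a descriptive plan.

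The plan also has partial cover. Section 11.6 promises listings and defines a baseline for every outcome variable, so the linkage could be made at reporting. That is true, but no neurological listing is named, and a listing is not a pre-specified summary.

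Finally, the pooled population matches the stated hypothesis, and staying free of encephalopathy is itself relevant. That is a reason to keep the pooled summary and to report new encephalopathy separately.

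**Conclusion.** The point holds as a modest one. Section 11 gives no within-patient change or shift summary for the neurological scales. Its visit tables mix patients with and without encephalopathy to improve, so as written they do not show how many patients improved. This rests on the text alone, plus the ordinary meaning of the best West Haven grade.

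The size is illustrative: a pooled rate would be (1 − g) times the rate among encephalopathic patients, so an assumed 60% reads 54%, 42% or 30% at g = 10%, 30% or 50%. It should not be read as a predicted bias in a reported result.

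The study has no control group, is descriptive and is not powered (Synopsis, Statistical Considerations; Section 11.3). The change improves what the description can answer. It cannot establish a drug effect, separate one from natural recovery, or establish a cohort difference. It is an optional, low-cost improvement to an exploratory endpoint.

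**What to change.** Add to Section 11.6:

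- West Haven as shift tables from the pre-infusion baseline grade (Section 8.2) to the grade at each scheduled assessment, overall and by cohort.
- Improvement on West Haven, and change in Glasgow Coma Scale and O-log, among patients with encephalopathy at that baseline. Use the baseline battery and not the ALF/ALI entry label, because up to 32 h may pass between consent and infusion (Section 7.4).
- The number and proportion of patients without baseline encephalopathy who develop it.
- The pooled summary, kept alongside.
- The populations: PP, with the ITT sensitivity analysis already planned in Section 11.4.

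The scores are already collected, so the cost is a paragraph and a few tables. The drawback is smaller denominators and wider intervals, as Step 5 of the working shows.

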5 INVESTIGATIONAL PLAN

5.1 *Study Design*

This is a Phase 2a, multi-center, open-label study, conducted in two cohorts in patients

diagnosed with acute liver failure/severe acute liver injury (ALF/ALI) who meet inclusion/exclusion criteria. The acetaminophen adduct assay will be used as an additional test for equivocal or presumed cases of acetaminophen toxicity, where the history is not substantiated and the assay for acetaminophen itself proves to be negative.

Up to 36 evaluable patients are planned to be enrolled in two cohorts:

Cohort 1 will include patients with ALF/ALI with minimal renal dysfunction at the time of enrollment (defined as serum creatinine ≤ 1.5 mg/dL and mean arterial pressure of >65 mmHg).

Cohort 2 will include patients with ALF/ALI with compromised renal function (defined as a serum creatinine >1.5 mg/dL and <10 mg/dL) and mean arterial pressure of >65 mmHg.

Informed consent will be obtained from the patient and/or patient's legally authorized representative or family member [as defined in 21CFR50.3(m)]. All patients will receive medical care for acute liver failure/severe acute liver injury according to the institution's standards of care. Standard of care may include, but is not limited to, administration of NAC and consideration for orthotopic liver transplantation. All patients in Cohort 2 with a serum Cr level of ≥ 2.0 will be considered for placement on continuous veno-venous hemodialysis (CVVHD) for an appropriate interval as standard of care for this condition.

The initial dose of OCR-002 will be initiated once consent is obtained, all eligibility criteria are confirmed to be met and all baseline measurements have been completed. The infusion may begin after obtaining signed informed consent; or, up to 32 h after obtaining consent should the time be necessary to complete any pre-study drug initiation requirements and/or to provide a time frame for study drug administration.

Treatment Day 1-Time "0" (T0) is the start of the initial infusion. At this time, each patient in Dose Levels 1 through 3 will receive an initial infusion rate of OCR-002; thereafter, up and down titration decisions will be based on patient tolerability, clinical safety assessments (refer to Treatment below), and the patient's status within the assigned dose level. Each dose escalation will be administered to Cohort 1 patients and safety and PK data reviewed and approved by the SRC prior to exposing Cohort 2 patients to the study drug and subsequent dosing levels. A dedicated intravenous infusion line for the study drug is the recommended option.

The SRC will review all safety and PK data for the first six evaluable Cohort 1 patients at Dose Level 1 and at Dose Level 2 to determine if Cohort 2 patients may be enrolled to receive study drug at Dose Level 1.

If patient safety is confirmed, three Cohort 1 patients may be enrolled to receive study drug escalation to Dose Level 3. Concurrent with enrollment of Cohort 1 patients in Dose Level 3, three Cohort 2 patients may be enrolled at Dose Level 1. If patient safety is confirmed for Cohort 2 Dose Level 1, three Cohort 2 patients may be enrolled at Dose Level 2.

Once three Cohort 1 patients complete Dose Level 3, the SRC will review the safety and PK data in both Cohort 1 and Cohort 2 patients. If patient safety is confirmed in both Cohorts and at each dosing level, enrollment will be open to both Cohort 1 and Cohort 2 patients to receive Dose Level 3.

After at least three evaluable Cohort 1 patients complete Dose Level 3 and the data are reviewed by the SRC, Cohort 1 patients may be enrolled to receive study drug at Dose Level 4. Similarly, after at least three evaluable Cohort 2 patients complete Dose Level 3, Cohort 2 patients may be enrolled to receive study drug at Dose Level 4, once the safety and PK data are reviewed and approved by the SRC.

Patients may have an IV catheter inserted for ease of obtaining safety, PK and PD blood sampling. Blood samples for measurement of plasma ornithine, phenylacetate and PAGN concentrations will be collected at multiple time-points during the infusion period, at the Completion of the Last Infusion, and 24 hours Following the Completion of the Last Infusion. Urine samples will be collected at specific intervals to determine the amount of PAGN excreted/synthesized.

Patients will be assessed for safety and exploratory efficacy of OCR-002 as well as pharmacokinetic and pharmacodynamic variables for up to a 6-day period which includes up to 5 days (maximum of 120 h) of infusion, at the Completion of the Last Infusion, and at 24 hours Following the Completion of the Last Infusion. Patients also will be assessed at the Day 30 post treatment period. The total intended enrollment is approximately 18 patients with minimal renal dysfunction and approximately 18 with compromised renal function. Enrollment will be discontinued when 36 evaluable patients are enrolled.

Supportive Care

Inotropic support may be used to maintain mean arterial pressure above 65 mmHg in patients who are hypotensive either before or after enrollment. Dialysis or continuous veno-venous hemofiltration (CVVH), endotracheal intubation and mechanical ventilation will be considered as indicated. Cerebral edema will be managed according to local practice with mannitol or hypertonic saline. Antibiotic therapy may be initiated and modified as required. In patients who have intracranial pressure (ICP) monitors placed, as determined by standard of care at each institution, the ICP (if available) and cerebral perfusion pressure will be monitored continuously, in addition to the mean arterial pressure, and reported hourly during the period of active study drug infusion.

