Study	Up to 36 evaluable male and female patients aged 18 to 65 years (have not reached

Population	their 66th birthday) with acute liver failure or severe acute liver injury will participate.
Key Inclusion Criteria	
 1. Men and women, ages 18-65 (have not reached their 66th birthday). 2. Acute liver failure, defined as the development of coagulopathy (International normalized ratio [INR] ≥ 1.5) with encephalopathy in a patient with no prior history of liver disease with onset of symptoms within 28 days of the inciting event. Patients may have either a history of acetaminophen overdose (defined as >4 g/day within 7 days of presentation) and/or detectable acetaminophen levels in the serum, with a pattern of liver function tests typical for acetaminophen toxicity (bilirubin < 10 mg/dL and alanine aminotransferase (ALT) ≥ 1000 IU/L), or a diagnosis of hepatitis A, hepatitis B, drug-induced liver injury, autoimmune hepatitis or indeterminate cause based on standard criteria; refer to Section 6.2.1 for the definitions of standard criteria for these diagnoses. 3. ALI patients may also be enrolled (those meeting the above criteria plus coagulopathy (INR ≥ 2.0) and no evidence of encephalopathy and may provide consent themselves. 4. Written informed consent from the patient or patient's legally authorized representative or family member as defined in 21CFR50.3(m)--if he/she has evidence of encephalopathy (ALF). 5. Ammonia level ≥ 60 μmol/L at baseline (within 8 hrs prior to infusion start time). 6. Serum creatinine levels as follows: 
 a. Cohort 1: Creatinine ≤ 1.5 mg/dL; and b. Cohort 2: Creatinine >1.5 mg/dL and < 10 mg/dL. 7. Mean arterial pressure of >65 mmHg.

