3.3.2 Rationale for Dose Selection

Ocera Therapeutics, Inc. (Durham, NC) has conducted two clinical trials evaluating safety, tolerability and pharmacokinetics in healthy volunteers (n=48) and stable cirrhotic patients (n=43).

Clinical study OCR-002 HE201 was designed as a randomized, placebo-controlled, dose-ranging study, evaluating doses (i.v. infusion) of 1, 3, 10, 20 and 30g given over 4h, and 30, 40 and 60g given over 24h. Following a single ascending dose phase, a multiple ascending dose phase (5d of consecutive administration) for doses of 1, 3, 10 and 20g given over 4h was assessed. The key findings in this study included:

There were no deaths, SAE or AE discontinuations in the study.

A dose related increase in the incidence and severity of adverse events was observed.

Commonly occurring adverse events that appeared to be related to dose included dizziness, somnolence, headache, nausea/vomiting and tinnitus.

There was no evidence to suggest that AEs increased or new AEs occur with multiple dosing.

With respect to blood pressure, there were no apparent trends from placebo with respect to mean changes from baseline; however at dose levels $\geq 20\text{g}/4\text{h}$, several patients experienced clinically significant orthostatic hypotension.

There appeared to be a dose and exposure related increase in mean heart rate starting at a dose level of $10\text{g}/4\text{h}$ and higher. These effects also persisted for longer periods in the higher dose groups.

20g administered over 4 h was the maximum tolerated dose (MTD), however, doses of $10\text{g}/4\text{h}$ and below were well tolerated.

24h Holter monitor recording identified a dose-related increase in heart rate accompanied by modest effects on ventricular repolarization as measured by QT. These effects should be interpreted with caution in light of the small sample size and higher heart rates observed in this study.

There were no clinically significant abnormal laboratory parameters and no patient had any clinically significant changes in physical examination findings or mean

change in body weight between baseline and follow up.

Doses higher than 10g/4h are associated with adverse effects that may be rate and C_{max} related and are likely associated with the non-linear pharmacokinetic profile of phenylacetate above 10 g.

A slower infusion rate (24hr-infusion) avoids C_{max} related adverse effects while providing similar excretion of PAGN.

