6.2.2 Exclusion Criteria

1. History of chronic liver disease.
2. Signs of overt cerebral herniation, or uncontrolled intracranial hypertension by ICP monitoring (if applicable).
3. Evidence of Wilson's disease, alcoholic hepatitis, biliary obstruction, ischemic hepatitis, severe acute renal tubular necrosis (ATN) due to shock, or any patient with ongoing hypotension.
4. Significant gastrointestinal bleeding (coffee grounds per nasogastric tube and/or melena).
5. Hemodynamic instability, defined by a mean arterial pressure of $<$ 65 mmHg.
6. Cardiopulmonary complications such as pulmonary edema, aspiration pneumonia, heart failure.
7. QT interval of $>$ 500 msec at baseline ECG.
8. Pregnancy.
9. History of malignancy that has not been cured or any cancer in remission for less than 1 year. Non-melanoma skin cancers do not preclude participation in the trial.

10. Concomitant administration of drugs known to interfere with renal excretion of phenylacetylglutamine or those medications that may induce hyperammonemia such as haloperidol, valproic acid and systemic corticosteroids (prohibited during the study). Alternative ammonia modifying agents such as lactulose and rifaximin are not considered standard of care and are prohibited during the study period.
11. Any other health condition that would preclude participation in the study in the judgment of the principal investigator.

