11.7.3 Vital Signs

Vital signs results (systolic and diastolic blood pressure, pulse rate and body temperature) will be listed for individual patients. Each vital sign measure will be tabulated by evaluation time point. Baseline for vital signs measurements will be defined as the last evaluation before the beginning of the first OCR-002 infusion (which will generally be Baseline, pre-dose). Summary statistics, including mean absolute change from baseline, will be determined and tabulated for each measure.

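### The vital-sign summaries in Section 11.7.3 ignore inotropic support and so attenuate any fall in blood pressure on OCR-002; the plan also leaves open whether the qualifying MAP is judged on or off support.

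*Combined protocol and SAP*

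**What the plan says.** **Support.** The synopsis and Section 5.1 (Supportive Care) allow it: "Inotropic support may be used to maintain mean arterial pressure above 65 mmHg in patients who are hypotensive either before or after enrollment".

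**Eligibility.** Inclusion criterion 7 (synopsis and 6.2.1) asks for "Mean arterial pressure of >65 mmHg". In 6.2.2, exclusion 5 removes patients with a MAP under 65 mmHg, and the last clause of exclusion 3 removes "or any patient with ongoing hypotension". None of these says whether pressure is read with or without inotropes, and the duration or state that makes hypotension ongoing is not defined.

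**Analysis.** Section 11.7.3 says: "Vital signs results (systolic and diastolic blood pressure, pulse rate and body temperature) will be listed for individual patients". It tabulates each measure by time point and adds: "Summary statistics, including mean absolute change from baseline, will be determined and tabulated for each measure". Section 11.6 supplies SD, median, minimum and maximum for continuous variables. Section 8.3 has MAP monitored and collected continuously during treatment, and 7.6 has all concomitant medications recorded. Neither MAP nor inotrope use is analysed in Section 11. The memorandum at the end of the document confirms that there is no separate SAP.

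**Known effect.** Section 9.1.2 lists hypotension and tachycardia among the reactions expected with the drug. Section 3.3.2 reports that in the earlier dose-ranging study, at 20 g over 4 h and above, "several patients experienced clinically significant orthostatic hypotension".

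**The concern.** Safety and tolerability is the primary objective, and hypotension is a listed reaction to the drug. The planned summary looks at pressure after the clinician has acted on it. Once support is given, a low reading is replaced by one near the target, the mean moves towards no change, and the patients with the largest falls lose the most. Inotropes can also affect pulse rate, the other listed haemodynamic reaction.

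If a patient is already supported when the infusion starts, the baseline is itself a supported value. More support to hold the same pressure then leaves the change from baseline near zero.

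At stake are the Safety Review Committee's reading of dose groups that start with three patients, and the final description of haemodynamic tolerability.

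**Working it through.** The plan gives no figure here to reproduce, so the check is mainly a comparison of sections, with one labelled illustration of size.

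**1. Does mean change detect this drug's effect?** Section 3.3.2 reports two things about the same study: mean blood-pressure change showed no apparent trend against placebo, and individual patients had clinically significant orthostatic hypotension. By the protocol's own account, mean change can miss the effect.

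**2. When is pressure read?** Section 8.3 schedules vital signs on treatment at 12, 24, 36, 48, 72 and 96 h, at the end of infusion, and 24 h later. The gaps are 12 h up to 48 h, and up to 24 h after that. A fall corrected between visits enters no scheduled value, so the listing, minimum and maximum do not show it either.

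**3. How large could the attenuation be? (All inputs assumed.)** For one patient, take a baseline MAP of 70, an unsupported value of 50 and a supported value of 65. The true change is 50 − 70 = −20 and the recorded change is 65 − 70 = −5, a difference of 15 mmHg.

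For a group, assume baseline MAP is normal with SD 10, keeping only values above 65. Unsupported MAP is baseline minus the true fall, plus noise of SD 8. Observed MAP is the larger of the unsupported value and 65. Simulated results:

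| Mean before truncation | True change | Observed change | Retained | Unsupported MAP ≤65 |
|---|---|---|---|---|
| 75 | −5 | −3.5 | 70% | 25% |
| 75 | −10 | −6.8 | 68% | 41% |
| 75 | −15 | −9.3 | 62% | 59% |
| 80 | −5 | −4.0 | 80% | 17% |
| 80 | −10 | −7.8 | 78% | 30% |
| 80 | −15 | −10.9 | 73% | 46% |
| 85 | −5 | −4.4 | 89% | 10% |
| 85 | −10 | −8.7 | 87% | 20% |
| 85 | −15 | −12.4 | 82% | 33% |

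The mean change is reduced, not abolished. The illustration is in MAP, whereas 11.7.3 summarises systolic and diastolic pressure, so it shows direction and rough order only.

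**4. Do the other routes close the gap?** Section 11.7.1 tabulates adverse events, and hypotension can appear there. But 9.1.2 lists it as expected from ALF/ALI as well as from the drug, there is no control arm, and causality is the investigator's judgement. Under 9.1.3, a condition present before infusion becomes an event only if the investigator judges that it has worsened or changed in character. The suspension trigger in 9.7.1 counts unexpected SAEs. The synopsis escalation rule is not limited to unexpected events, but it counts only SAEs that the investigator does not attribute to liver failure. A patient stopped for shock before 72 h leaves the per-protocol set, which 11.4 makes primary for all outcomes.

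**5. Eligibility, worked on one case.** Take a patient with MAP 68 on inotropes. Inclusion 7 is met (68 > 65). Exclusion 5 is not triggered (68 is not below 65). Exclusion 3 turns on whether hypotension held off by a drug counts as ongoing. The Supportive Care text foresees support before enrollment. Two sites can reasonably decide differently, and the answer determines whether the baseline is supported.

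**6. What a count of supported patients would deliver.** Exact 95% intervals for assumed event counts are: 0/3, 0–70.8%; 0/18, 0–18.5%; 3/18, 3.6–41.4%; 6/36, 6.4–32.8%. These are descriptive, in keeping with the plan.

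**The case against.** A reader might infer that blood-pressure safety rests on mean change alone, or that hypotension would be hidden altogether. The documents do not support either reading. Section 11.7.3 lists individual values and tabulates them by time point, and 11.6 adds minimum and maximum. Any unfavourable sign is an adverse event (9.1.1), one that needs medication fits Grade 2 (9.4), and worsening of a pre-existing condition is reportable (9.1.3, 9.8). Shock is a listed reason to stop treatment (6.3.4), and the medical monitors follow event rates and can alert the Safety Review Committee (9.7). Section 11.7.5 also records heart rate daily in relation to the start of infusion. All of this stands. It makes the problem one of attenuation in the vital-sign summaries, with a partial and judgement-dependent backstop.

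The earlier hypotension arose at much higher rates: 20 g/4 h is 5 g/h, about 6 times the highest rate here (5/0.83 = 6.0). The heart-rate rise began at 10 g/4 h, or 2.5 g/h, about 3 times (2.5/0.83 = 3.0). Section 3.3.2 adds that slower infusion avoids peak-related effects. That stands too, and the true effect in this trial may be small. It does not make the summary a better way to find out, and hypotension remains on the drug's expected list.

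Two cautions about the remedy also stand. Splitting values by on or off support conditions on something that happens after treatment starts, so it would not estimate the drug effect. And the CRF is not shown: 7.6 does not mention dose changes of concomitant drugs, and hourly reporting of MAP is stated only for patients with intracranial pressure monitors.

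**Conclusion.** The point holds as a modest, worthwhile improvement. As written, the 11.7.3 summaries are pulled towards no effect whenever pressure is supported. Starting or raising support is a direct marker of the listed reaction, and it has no planned table.

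The size cannot be derived from the documents. The 62–89% retained, and the 15 mmHg for one patient, depend entirely on assumed baseline, fall, spread and a support target of 65 mmHg. Neither should be quoted as an estimate for this trial.

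Two stronger readings of the eligibility text are tempting. One is that the Supportive Care paragraph contradicts the exclusions. It does not do so outright, because a patient who was hypotensive earlier but has MAP above 65 on support can meet the literal limits. What remains is an unreconciled ambiguity about on- or off-support MAP and about ongoing hypotension. The other is that a MAP of exactly 65 falls between the criteria. It does not: such a patient fails inclusion 7, and 6.3.2 requires all criteria to be met.

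**What to change.** In 11.7.3, add the following by cohort and dose level for all treated patients:

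- the number and percent with a new start of an inotrope or vasopressor after T0 and, where the CRF records it, a dose increase, with the time from T0 and the OCR-002 infusion rate at onset;
- the lowest recorded MAP per patient, from the MAP data collected under 8.3;
- a flag for supported values in the blood-pressure and pulse listings. Any on/off-support display should be labelled descriptive and not presented as an estimate of drug effect.

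Separately, reconcile the Supportive Care text (synopsis and 5.1) with inclusion 7 and exclusions 3 and 5, so that the documents say whether the qualifying MAP is judged on or off support. Which rule to adopt is a clinical decision for the sponsor and investigators.

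The cost is a few extra tables, one clarification of eligibility wording, and a check that the CRF holds inotrope dose changes and how often MAP is recorded. No new patient procedure is needed. If dose changes are not captured, the table can be limited to new starts.
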